# Effect of Increasing Doses of Tiopronin on Cystine Capacity in Patients with Cystinuria

## 1. Synopsis

Protocol Number:	6421
Protocol Title:	Effect of Increasing Doses of Tiopronin on Cystine Capacity in Patients with Cystinuria
Study Chair:	[name]
Statistician:	[name]
Consortium:	Rare Kidney Stone Consortium
Participating Sites:	New York University Langone Health, New York, NY
Activation Date:	09/10/2018
Sample Size:	15 subjects
Target Enrollment Period:	1 year
Study Design:	Crossover trial of escalating doses
Primary Study Objective:	To evaluate the effect of escalating doses of cystine binding thiol drugs on the cystine capacity of the urine. The overall goal will be to help guide therapy and ultimately minimize unnecessary side effects caused by larger dosages.
Secondary Study Objective(s):	None.
Study Population and Main Eligibility/ Exclusion Criteria:	Eligibility: Patients between ages 18-80 with confirmed diagnosis of cystinuria with a medical regimen that includes Tiopronin who are willing to complete a 24h urine collection and food diary. Female patients at childbearing age who are willing to use a contraception method. Exclusion Criteria: Patients who are unwilling or unable to provide informed consent, pregnancy, patients with renal colic or patients who are scheduled for a urological procedure.
Treatment	
Agent-	Tiopronin
Dosage, schedule, route of administration-	500mg PO daily x 7 days, then 500 mg PO BID x 7 days, then 1g PO BID x 7 days
Safety Issues-	Allergy or drug side effects
Primary Outcome Measures:	Urine cystine capacity
Secondary Outcome Measures:	Urine volume, pH, urea, sodium, creatinine, cystine concentration, and urinary cystine supersaturation
Statistical Considerations (sample size and analysis plan):	The impact of CBTD dose on CysCap will be analyzed with a mixed effects model, with subject as a repeated factor, and including dose and period effects.

Sponsors (federal, state, foundation and industry support):	National Institutes of Health (NIH), NIDDK, ORDR
--	--

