#### **4 Study Design and Methods**

Due to the low prevalence of cystinuria in the population, the number of patients available to participate in this study precludes the ability to conduct a randomized controlled trial with satisfactory probability to achieve a projected sample size. As in our recently completed study, we plan to enroll 5-10 patients in the study and perform a crossover trial in which patients receive escalating dosages of CBTDs.

Patients will be recruited from the clinical practice of the principle investigator at routine clinic visits at the Kidney Stone Prevention Clinic at NYU Langone Health. After completing informed consent, the patient will have an initial visit that will be a screening interview. During this interview, the patient will be screened for symptoms of renal colic (which if present would exclude him/her from eligibility), as well as asked about any scheduled urologic procedures. A medication history will be taken at this time, and the subject's most recent bloodwork (including a complete blood count) and most recent urinalysis will be reviewed. The total time for this visit should be approximately 20 minutes. The remainder of the study will be performed at home.

There will be four parts to the study. Each part will be divided into a 7-day period in which patients will be taking different dosage of Tiopronin and will have a urine collection at the end of each period. Patients will stop taking their medications for one week in the first part. The dosage of Tiopronin in the following parts will be as follow: 500 mg for the second part, 1g for the third part and 2g for the third part. Unlike the previous study, there will not be a 3g dosage week.

A 24-hour urine collection will be performed on day 7 of each study period. The order in which the four parts of the study are performed will be randomized for each subject, in order to prevent an order effect. After a subject is enrolled in the study, the order in which he/she will perform the study periods will be determined by a computer program that generates a random order of the numbers 1-4. There will not be a specified wash-out period in between study periods due to the short half-life of Tiopronin. With the exception of Tiopronin, the patients will continue all of their regular medications including alkali therapy.

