Patients will continue on their self-selected ad-lib diets. They will keep a food diary during the day before the urine collection and during the urine collection. They will then replicate the diet during each of the subsequent parts of the study, repeating the same diet on the day before and the day of the urine collection. We will collect the food diaries at the end of the study to ensure compliance and to keep a record of what the subjects were eating.

The urine will be collected with thymol and gentamicin as preservatives, and maintained at room temperature. The urine will be alkalinized at home with 10g of NaHCO3 as per the usual Litholink protocol for cystine measurement. Study participants will be asked to measure the volume of their urine and then mail an aliquot of their urine to a commercial laboratory, Litholink Corporation (Chicago, IL), for analysis. Another specimen will be mailed to Mayo Clinic for liquid chromatography mass spectrometry (LC/MS) testing.

The urine pH, sodium, urea, and creatinine will be measured by Litholink. Additionally, the cystine supersaturation, 24h urine cystine excretion and cystine capacity of each urine sample will be measured by the following method, the “solid phase” cystine assay. Measured amounts of cystine crystals will be incubated in the urine at 37°C for 48 hours with stirring. The residual solid phase will then be harvested by centrifugation at 3800 rpm for 20 minutes at room temperature and then dissolved in 25ml of high-pH buffer (0.1 M sodium carbonate; pH 9.9). The cystine concentration will be measured in both the supernatant liquid and the buffer to determine the change in solid phase, which is known as the cystine capacity.

The primary outcome of the study is to determine the effect of drug dosage on urinary cystine capacity. Thus, the mean cystine capacities in each part of the study (0 g/d, 500 mg/d, 1 g/d, and 2 g/d) will be compared. Urine urea, a surrogate of protein intake and urine sodium will be measured and compared to ensure diets are replicated correctly throughout the study period. Urine pH will be also measured to make sure similar amounts of alkali therapy are used in each part of the study.

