### 5.1 Study Oversight:

The Study Chair has primary oversight responsibility of this clinical trial. The NIH appointed Data Safety Monitoring Board (DSMB) has oversight responsibility of the Data Safety Monitoring Plan (DSMP) for this clinical trial. The DSMB will review accrual, patterns and frequencies of all adverse events, and protocol compliance every 6 months. The D/OSMB makes recommendations to the NIH regarding the continuation status of the protocol.

Each site's Principal Investigator and their research team (co-Investigators, research nurses, clinical trial coordinators, and data managers) are responsible for identifying adverse events. Either the Principal Investigator or one of the co-Investigators will call each subject weekly during the study period to remind them to change the dose of medication, and to assess for any potential adverse events. All subjects will undergo a blood test for complete blood count and urine test for urinalysis within one month of completing the study to monitor for any adverse effects from the changes in medication dosages. The results of the blood and urine tests will be reviewed by the Principal Investigator. All adverse events will be reported to the DSMB. Aggregate report- detailed by severity, attribution (expected or unexpected), and relationship to the study drug/study procedures – will be available from the DMCC for site review. The research

team will then evaluate whether the protocol or informed consent document requires revision based on the reports.

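### The synopsis gives a fixed ascending schedule with no 0 g week, against the randomised four-part order in Section 4: align the two, and preferably draw orders from balanced sequences

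*Combined protocol and SAP*

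**What the plan says.** The synopsis names the design as "Crossover trial of escalating doses" and gives the dosing as "500mg PO daily x 7 days, then 500 mg PO BID x 7 days, then 1g PO BID x 7 days". In daily totals that is 0.5, then 1, then 2 g, in three successive weeks.

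Section 4 (Study Design and Methods) describes four 7-day parts, the first of them off Tiopronin. Their order "will be randomized for each subject, in order to prevent an order effect", and is "determined by a computer program that generates a random order of the numbers 1-4". The primary outcome paragraph of the same section states that "the mean cystine capacities in each part of the study (0 g/d, 500 mg/d, 1 g/d, and 2 g/d) will be compared".

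Section 4 is not fully consistent either. It says the plan is to "perform a crossover trial in which patients receive escalating dosages of CBTDs", and it assigns the doses as "500 mg for the second part, 1g for the third part and 2g for the third part", so two doses share one label and no part is called the fourth.

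Section 6 specifies a mixed model with subject as the repeated factor and with effects of dose and period. Section 5.1 says that an investigator "will call each subject weekly during the study period to remind them to change the dose of medication".

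**The concern.** The synopsis and Section 4 give different treatment rules, and both are current text. They differ in the number of periods (three or four), in whether there is an untreated week, and in whether the order is fixed or random.

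The order matters because the primary model adjusts for period. If every subject takes the doses in the same order, a dose effect and a trend over the weeks produce the same data, and the model cannot tell them apart. Patients are treated at home and are prompted by weekly calls, so the order actually taken depends on the schedule the caller works from. Nothing in the documents shows that anyone would use the synopsis in place of the generated order. The risk is conditional on that.

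The second matter is efficiency. An independent random order for each subject is unbiased, but in a trial this small it can spread the doses unevenly over the four weeks, which costs precision once period is in the model. No carry-over bias is alleged: the plan cites a short half-life and collects urine on day 7 of each period.

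**Working it through.** **Inputs.** Four doses (0, 0.5, 1, 2 g/d) and four periods, from Section 4. Model terms (subject, period, dose), from Section 6. Sample sizes: 15 planned and 9 required, from the sample size paragraph of Section 6, and 10 as the upper end of the 5 to 10 given in Section 4. The plan offers no figure on this point to reproduce.

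**1. Common ascending order, period as a factor.** Write the mean for subject i in period j as s_i + p_j + d_k, where k is the dose taken. If all subjects ascend, k = j, so p_j and d_j appear only as the sum p_j + d_j.

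- Four periods with 0 g first, n = 15: columns 15 + 3 + 3 = 21, rank 15 + 3 = 18.
- Same, n = 9: columns 9 + 3 + 3 = 15, rank 12.
- The synopsis's literal three periods, n = 15: columns 15 + 2 + 2 = 19, rank 15 + 2 = 17.

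In each case the shortfall equals the number of dose parameters, so no dose contrast is estimable.

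**2. Common ascending order, linear period.** The mean is s_i + βj + d_j. Adding c·j to d_j and subtracting c from β changes nothing, so a contrast Σ c_j d_j is estimable only if Σ c_j j = 0. For a pair of doses in periods a < b this sum is b − a. Over the six pairs it takes the values 1, 2, 3, 1, 2, 1 and is never zero. The rank is 18 of 19 columns at n = 15 and 12 of 13 at n = 9. Two degrees of freedom for dose survive, but none of the six pairwise differences does.

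**3. Section 4 order.** Each subject gets an independent random permutation of the four doses (20,000 simulated trials per n). The model was estimable in every draw at n = 15. R is the variance of a period-adjusted pairwise dose contrast, averaged over the six pairs and divided by the balanced-design value 2σ²/n. The SE ratio is √R, and n/R is the equivalent number of subjects in a balanced design. The last column allocates subjects in permuted blocks of four to the sequences of a Williams square (2,000 draws).

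| n | R, unrestricted | √R | n/R | Draws with an empty dose-by-period cell | R, blocked Williams |
|---|---|---|---|---|---|
| 15 | 1.080 | 1.039 | 13.9 | 19% | 1.0045 |
| 10 | 1.132 | 1.064 | 8.8 | 60% | 1.0137 |
| 9 | 1.153 | 1.074 | 7.8 | 71% | 1.0125 |

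The empty-cell figures can be checked roughly by hand. A given dose misses a given period with probability (3/4)^n, and there are 16 cells. The expected number of empty cells is 16 × 0.0134 = 0.21 at n = 15 and 16 × 0.0751 = 1.20 at n = 9. Blocked Williams allocation gives R = 1 exactly at n = 12.

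**4. The proposed square.** The sequences are 0–0.5–2–1, 0.5–1–0–2, 1–2–0.5–0 and 2–0–1–0.5 g/d. Each dose occurs once in each period, and each of the 12 ordered pairs of different doses occurs once as neighbours. This is a Williams square.

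**The case against.** The strongest reply is that the harm is hypothetical. Section 4 is explicit about randomisation, and the rest of the protocol supports four periods: payment for four stages (Section 4), a four-week duration (4.3), urine collections on days 7, 14, 21 and 28 (4.4) and a discussion of the week off drug (5.3). The synopsis row lists regimens of the agent, so an off-drug week could naturally be left out. The word escalating can describe a set of dose levels, and the repeated third part is an obvious slip, since Section 4 lists the four doses in the same order twice. Most of this stands, and it is why the problem is one of alignment and not a flaw in the operative design. It does not remove the conflict, because a schedule written with successive thens sets an order in time.

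It can also be said that the rank of 18 of 21 adds a 0 g week that the synopsis lacks. That is true, but the literal three-period schedule fails in the same way (17 of 19).

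On balancing, the gain at the planned 15 is small: 15 − 13.9 = 1.1 subjects, in a trial that enrols 15 against a stated need of 9. The model has no carry-over term, so any blocked Latin square would give the same period balance. Both points stand. The Williams form adds balance over the preceding dose at no extra cost, but it is a preference and not a necessity.

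**Conclusion.** The concern holds. The synopsis schedule is wrong as written: it contradicts Section 4 in the number of periods, the untreated week and the ordering. If it were followed, no pairwise dose difference could be estimated under the Section 6 model, with period either as a factor or as a linear trend. The replicated diet and the urea, sodium and pH checks may reduce a time trend, but they cannot make that model estimable. Under the Section 4 order the problem does not arise. This should be fixed; the rank results need no distributional assumption.

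The unrestricted generator is valid. Balancing it is a cheap improvement worth about 4% in standard error at n = 15 and 7% at n = 9. Those figures assume additive effects, independent within-subject errors of equal variance, and complete data. Dropout was not simulated.

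**What to change.** **Wording (should be done).**

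- In the synopsis, state four 7-day periods at 0, 0.5, 1 and 2 g/d, in an order randomised for each subject.
- In the synopsis and Section 4, delete escalating or define it as the set of dose levels.
- In Section 4, label 2 g as the fourth part, so that numbers 1 to 4 map to 0, 0.5, 1 and 2 g/d.

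This costs nothing beyond the edit.

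**Balanced sequences (optional improvement).** Replace the unrestricted order with random allocation, in blocks of four, to the four Williams sequences listed above. This needs a prepared list and no extra patients, visits or tests. The downsides are small. There are 4 distinct sequences in place of 24, and balance is exact only when enrolment is a multiple of four, so it is near-exact at 15 or after dropouts. The last allocation in a block is predictable, which matters little when every subject takes every dose and the endpoint is a laboratory assay.

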## 1.1 Overview:

The purpose of this study is to determine the minimum effective dose of the cysteine binding thiol drug (CBTD) Tiopronin on urine cystine capacity, which is a measure of cystine solubility in the urine, in patients with cystinuria.

Cystinuria is a rare genetic disease that can lead to significant morbidity in affected patients due to the recurrent nature of the disease. As a result, a significant part of treatment is focused on prevention of stone formation. Current methods of prevention include increasing fluid intake, dietary modifications, alkali therapy, and CBTDs, which help increase the solubility of cystine in the urine. At present, the dosing of Tiopronin is empiric, and the drug not titrated to a specific measured effect. We propose to follow the level of urine cystine capacity in order to help guide treatment and to use lower than usually prescribed Tiopronin doses to decrease the potential side effects while keeping the same therapeutic benefit. This will increase adherence with the medications by decreasing the burden of the large number of pills that need to be taken daily.

## 2 Specific Aims (Hypothesis and Objectives)

Our primary objective is to compare the effect of different Tiopronin doses on urinary cystine capacity (CysCap). A positive urinary cystine capacity reflects the ability of the urine to take up more cystine and therefore decrease the risk of stone formation. In a previous study, we demonstrated that Tiopronin improves cystine capacity and that the change in cystine capacity was minimal with doses above 1g.

We propose comparing the effects of lower doses of Tiopronin on cystine capacity.

## 3 Background

Cystinuria accounts for approximately 1% of kidney stones in adults and 6% to 8% in children. It is an autosomal recessive disorder that leads to an impairment in the renal and intestinal transport of cystine and dibasic amino acids: ornithine, arginine, and lysine. As a result of the poor solubility of cystine, the increased urinary excretion leads to precipitation of cystine in the renal tubules, resulting in nephrolithiasis. The recurrent nature of the stones in this disorder can lead to significant morbidity in these patients.

Measurements of cystine excretion in the urine are inaccurate. The assays cannot reliably distinguish between the thiol groups of cystine and the thiol groups of CBTDs either free or bound to cysteine. Prior studies also found that measurements of cystine solubility varied with pH, and therefore nomograms to determine cystine supersaturation could not accurately be made. A recent assay for cystine capacity is a promising new tool that directly measures the ability of the urine to take up additional cystine from a preformed solid phase (undersaturation,

or positive cystine capacity) or give it up to the solid phase (supersaturation, or negative cystine capacity). In contrast to previous assays, the CysCap assay accurately measures cystine solubility in the presence of CBTDs.

Current treatment strategies to prevent stone formation in patients with cystinuria include increasing fluid intake, alkalinizing urine with alkali therapy, and CBTDs such as Tiopronin (Thiola), D-penicillamine, and Captopril. These medications have sulfhydryl groups that can reduce the disulfide bond in the dimer cystine and produce mixed disulfides with the monomer cysteine that are more soluble than the homodimer itself.

Our study by Dolin, et al, showed that CBTDs significantly increased the cystine capacity of urine compared to the control period without CBTDs. We tested the effect of different doses of CBTDs used in clinical practice (1g, 2g, 3g) on cystine capacity in a previous study and concluded that there was no change in cystine capacity with doses above 1g. The higher doses were well tolerated but had little efficacy in changing CysCap. We also retrospectively realized that measuring Tiopronin in the urine would have been useful; in the current study, we will collect urine for that purpose.

We propose testing the minimum effective dose of Tiopronin by comparing doses lower than 2g. Reducing Tiopronin doses will ultimately minimize unnecessary side effects while keeping the same benefit.

#### **4 Study Design and Methods**

Due to the low prevalence of cystinuria in the population, the number of patients available to participate in this study precludes the ability to conduct a randomized controlled trial with satisfactory probability to achieve a projected sample size. As in our recently completed study, we plan to enroll 5-10 patients in the study and perform a crossover trial in which patients receive escalating dosages of CBTDs.

Patients will be recruited from the clinical practice of the principle investigator at routine clinic visits at the Kidney Stone Prevention Clinic at NYU Langone Health. After completing informed consent, the patient will have an initial visit that will be a screening interview. During this interview, the patient will be screened for symptoms of renal colic (which if present would exclude him/her from eligibility), as well as asked about any scheduled urologic procedures. A medication history will be taken at this time, and the subject's most recent bloodwork (including a complete blood count) and most recent urinalysis will be reviewed. The total time for this visit should be approximately 20 minutes. The remainder of the study will be performed at home.

There will be four parts to the study. Each part will be divided into a 7-day period in which patients will be taking different dosage of Tiopronin and will have a urine collection at the end of each period. Patients will stop taking their medications for one week in the first part. The dosage of Tiopronin in the following parts will be as follow: 500 mg for the second part, 1g for the third part and 2g for the third part. Unlike the previous study, there will not be a 3g dosage week.

A 24-hour urine collection will be performed on day 7 of each study period. The order in which the four parts of the study are performed will be randomized for each subject, in order to prevent an order effect. After a subject is enrolled in the study, the order in which he/she will perform the study periods will be determined by a computer program that generates a random order of the numbers 1-4. There will not be a specified wash-out period in between study periods due to the short half-life of Tiopronin. With the exception of Tiopronin, the patients will continue all of their regular medications including alkali therapy.

Patients will continue on their self-selected ad-lib diets. They will keep a food diary during the day before the urine collection and during the urine collection. They will then replicate the diet during each of the subsequent parts of the study, repeating the same diet on the day before and the day of the urine collection. We will collect the food diaries at the end of the study to ensure compliance and to keep a record of what the subjects were eating.

The urine will be collected with thymol and gentamicin as preservatives, and maintained at room temperature. The urine will be alkalinized at home with 10g of NaHCO3 as per the usual Litholink protocol for cystine measurement. Study participants will be asked to measure the volume of their urine and then mail an aliquot of their urine to a commercial laboratory, Litholink Corporation (Chicago, IL), for analysis. Another specimen will be mailed to Mayo Clinic for liquid chromatography mass spectrometry (LC/MS) testing.

The urine pH, sodium, urea, and creatinine will be measured by Litholink. Additionally, the cystine supersaturation, 24h urine cystine excretion and cystine capacity of each urine sample will be measured by the following method, the “solid phase” cystine assay. Measured amounts of cystine crystals will be incubated in the urine at 37°C for 48 hours with stirring. The residual solid phase will then be harvested by centrifugation at 3800 rpm for 20 minutes at room temperature and then dissolved in 25ml of high-pH buffer (0.1 M sodium carbonate; pH 9.9). The cystine concentration will be measured in both the supernatant liquid and the buffer to determine the change in solid phase, which is known as the cystine capacity.

The primary outcome of the study is to determine the effect of drug dosage on urinary cystine capacity. Thus, the mean cystine capacities in each part of the study (0 g/d, 500 mg/d, 1 g/d, and 2 g/d) will be compared. Urine urea, a surrogate of protein intake and urine sodium will be measured and compared to ensure diets are replicated correctly throughout the study period. Urine pH will be also measured to make sure similar amounts of alkali therapy are used in each part of the study.

Subjects will be asked to undergo a blood test (for complete blood count) and urine test (urinalysis) within one month of completing the study to monitor for any potential adverse effects of changing the dosages of medication. In our previous study of doses up to 3g no adverse effects were anticipated and none occurred. The laboratory tests may either be performed at an outside lab at the patient’s convenience, or in a routine office visit at the Kidney Stone Prevention Clinic at NYU Langone Health. If laboratory tests are performed at an outside laboratory, subjects will be asked to send the results to [name] for review.

As in the previous study, subjects will be reimbursed for any additional medication costs that they incur as a result of participating in the study. They will be compensated for the amount of \$25 per week, a total of \$100 only if they completed all 4 stages of the study. Litholink and Mayo Clinic testing will be performed at no cost to the patients and their insurance will not be billed.

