## **6 Statistical Considerations**

The impact of CBTD dose on CysCap will be analyzed with a mixed effects model, with subject as a repeated factor, and including dose and period effects.

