### **6421 Sample Size**

The primary endpoint is defined as a mean change in Cystine Capacity (CysCap). In a previous study, we saw the highest change in CysCap between dose 0mg/d vs. dose 1mg/d. With this large effect size, we would need 9 participants ( $P=0.05$ , power 85%) in this protocol. We plan to enroll 15 participants in this protocol. This should account for potential patient withdrawal or other unforeseen protocol issues.

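### Drawing each subject's dose order independently leaves dose and period unbalanced in a trial of 15 or fewer; a Williams square would recover about 4% in standard error at n=15 and 7% at n=9.

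*Combined protocol and SAP*

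**What the plan says.** Section 4 (Study Design and Methods) describes four one-week parts, each ending in a 24-hour urine collection. Their order "will be randomized for each subject, in order to prevent an order effect". The order for a given subject, fixed after enrolment, "will be determined by a computer program that generates a random order of the numbers 1-4". No Latin square, blocking or sequence list is mentioned anywhere. On wash-out, the same section says: "There will not be a specified wash-out period in between study periods". The reason given is the drug's short half-life.

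The comparison of interest, also in Section 4, is that "the mean cystine capacities in each part of the study (0 g/d, 500 mg/d, 1 g/d, and 2 g/d) will be compared". Section 6 (Statistical Considerations) specifies a mixed model with subject as a repeated factor, "including dose and period effects". The second Statistical Considerations paragraph, after the sample size, also names a Friedman test and GLS regression.

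The number of subjects is stated inconsistently. The sample size paragraph says "we would need 9 participants ( $P=0.05$ , power 85%) in this protocol" and "We plan to enroll 15 participants in this protocol", whereas Section 4 says "we plan to enroll 5-10 patients in the study".

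**The concern.** There are 24 possible orders of four doses. Drawing one independently for each of 15 or fewer people gives no assurance that each dose appears about equally often in each period, or that each dose follows each other dose about equally often. Balance holds only on average over hypothetical repetitions of the trial, not in the single list that will be used.

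Because period is in the model, any association between dose and period in the realised list inflates the variance of the dose contrasts. The Friedman test does not adjust for period, so there a chance imbalance would let a real period effect enter the observed dose comparison. With no wash-out, any carry-over would also fall unevenly across doses.

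The trial is small because the disease is rare, as Section 4 itself says. Its aim of finding a minimum effective dose depends on contrasts between active doses, which may be smaller than the contrast with no drug. Precision that costs almost nothing is worth keeping.

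**Working it through.** **Inputs.** Four doses and four periods, with independent random orders (Section 4). Model with subject, period and dose (Section 6). n = 15 or 9 (sample size paragraph) and 5 to 10 (Section 4). That the draws are unrestricted is inferred from the wording and from the absence of any balancing rule. The residual SD σ is not given and cancels from every ratio below.

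**The plan's own figure.** The 9 participants for 85% power cannot be reproduced, because no effect size, SD or sidedness is stated. Solving backwards for a paired t-test at 0.05, n=9 and 85% power imply a standardised paired difference of 1.14 (two-sided) or 0.98 (one-sided). The 1.14 is used below as an assumption.

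**Variance formula.** Let N be the 4x4 table of dose-by-period counts and D = N − n/4 its departure from balance. After adjustment for subject and period, the information on dose is

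C = n(I − J/4) − D Dᵀ/n,

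where I is the identity matrix and J the matrix of ones. The variance of the contrast between doses i and j is σ²(C⁻ᵢᵢ + C⁻ⱼⱼ − 2C⁻ᵢⱼ). If D = 0 this equals 2σ²/n, the ideal value (0.133σ² at n=15, 0.222σ² at n=9). Any non-zero D reduces C and so increases the variance.

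**Result.** Simulated lists of independent random orders (6,000 per n) were compared with Williams sequences cycled over the same n. Percentages are excess variance over Williams; the mean and 90th percentile refer to the average of the six dose contrasts.

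| n | Williams / ideal | Mean excess | 90th percentile | Mean excess in SE |
|---|---|---|---|---|
| 15 | 1.004 | 7.5% | 13% | about 4% |
| 12 | 1.000 | 10% | 18% | 5% |
| 10 | 1.014 | 12% | 22% | about 6% |
| 9 | 1.013 | 14% | 25% | about 7% |
| 5 | 1.042 | 31% | 64% | 14% |

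The worst of the six contrasts is on average 15% higher at n=15 (90th percentile 27%) and about 28% higher at n=9 (51%).

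In subjects, the mean loss is 15 − 15/1.075 = 1.0 at n=15 and 9 − 9/1.14 = 1.1 at n=9.

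**How uneven the lists are.** These figures describe the cause of the variance increase and are not a further loss.

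- In one given period at n=15, the chance that some dose goes to at most one subject follows by inclusion–exclusion. For one dose it is 0.75¹⁵ + 15(0.25)(0.75¹⁴) = 0.0134 + 0.0668 = 0.0802. Four times this is 0.321. Subtracting 0.013 for pairs of doses gives about 0.31.
- Some dose is missing altogether from some period in about 20% of lists at n=15 and about 70% at n=9.
- At n=15 the 16 dose-by-period counts run on average from about 1 to about 7. Under cycled Williams sequences they are all 3 or 4.
- At n=9, about 62% of lists contain at least one ordered pair of doses that never occurs consecutively.

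**Power.** Two-sided 0.05, residual degrees of freedom 4n − n − 3 − 3 = 3n − 6, effect in paired SDs (both effects are assumptions).

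| Effect | n | Williams | Random orders, mean |
|---|---|---|---|
| 1.14 | 15 | 99.0% | 98.5% |
| 1.14 | 9 | 90.1% | 86.2% (5th percentile 78%) |
| 0.8 | 15 | 85.4% | 82.9% |
| 0.8 | 9 | 62.4% | 57.4% |

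Power at n=9 exceeds 85% because this model has 21 residual degrees of freedom against 8 for the paired t-test.

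**Carry-over.** The figures above assume none. If a first-order carry-over term were added, which the plan does not do, the mean excess variance over Williams would be 17% at n=15 and 38% at n=9.

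**The case against.** The strongest reply is that the loss is small and nothing is invalid. Random order with a period term gives unbiased dose contrasts, so it does serve the stated purpose, only less efficiently. At the planned 15, the cost is about 4% in standard error and, at the effect implied by the plan's own sample size, half a percentage point of power. All of that stands, and it limits the weight of the point.

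The n=9 figure also needs a condition. In the sample size paragraph, 9 is the number required and 15 are enrolled to allow for withdrawal. If 15 were allocated in Williams blocks and six were lost at random (an assumption), the remaining Williams list would no longer be balanced. Its variance would be about 1.06 times ideal, and the excess for independent orders would fall from 14% to about 9%. The full 14% applies if exactly nine are allocated, which the range in Section 4 allows.

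Carry-over is a secondary matter. The protocol justifies omitting wash-out by the short half-life, and urine is collected only on day 7 of each period. The documents give no evidence that carry-over occurs. Balance would protect against it, but the case does not rest on it.

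Finally, the Synopsis lists an ascending schedule and calls the design one of escalating doses, while Section 4 randomises the order. Under one fixed order for everyone, dose and period would be completely confounded and balance across sequences would not arise. That is a larger problem than this one and needs its own resolution.

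**Conclusion.** The concern holds as a modest loss of efficiency, avoidable at almost no cost. Under the planned model, independent random orders raise the average variance of a dose contrast by 7.5% at n=15 and 14% at n=9 relative to a Williams square, and by 31% at n=5, the lower end of the range in Section 4. This assumes that the draws are unrestricted, that the order is randomised as Section 4 describes, that all allocated subjects complete four periods, and that there is no carry-over. With losses from 15 to 9 the excess is nearer 9%. The dose contrasts from the period-adjusted model remain unbiased. The change should be made, but the trial's validity does not depend on it.

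**What to change.** First reconcile the Synopsis with Section 4 on whether the order is ascending or randomised, and settle the planned number of subjects. If the order is randomised, replace the per-subject random permutation with random allocation to the four sequences of a 4x4 Williams square in randomly ordered blocks of four. With the four study parts assigned to letters at random, one such square is ABDC, BCAD, CDBA, DACB. Each letter appears once in each position and follows each other letter exactly once.

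Fifteen subjects give three complete squares and three sequences of a fourth. Exact balance needs a multiple of four, but at n=15 the shortfall is only 0.4% of variance. State the scheme in Section 4, and keep the period term in the primary model. Treat the Friedman test as supportive, since it ignores period.

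The cost is a different pre-generated list. Collections, model and sample size are unaffected. The one drawback is that the last sequence in a block can be deduced by anyone who knows the earlier ones. That matters little for an endpoint measured by an outside laboratory, and less still if the list is held away from those who enrol subjects.
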